16.0 Potential Benefits to Subjects

16.1 Describe the potential benefits that individual subjects may experience from taking part in the research. Include as may be useful for the IRB's consideration, the probability, magnitude, and duration of the potential benefits.

Participants in this study are HWs and PLWH. Overall, if successful, this project will yield a model for sustainable implementation of an intervention to reduce stigma and improve outcomes across the HIV cascade in resource-poor settings. Given the limited risks associated with this intervention study, the benefits outweigh the risks. PLWH are at particular risk of being stigmatized, yet few interventions exist that specifically reduce stigma in healthcare settings for the Caribbean. This study will ultimately benefit both PLWH and their healthcare providers by creating stigma-free healthcare environments and improving outcomes along the HIV continuum of care.

16.2 Indicate if there is no direct benefit. Do not include benefits to society or others. Also, payment to research subjects for participation in studies is not considered a benefit so do not list payment to research subjects in this section; if a recruitment incentive will be offered, described this in section 13 under Recruitment Methods.

There is no direct benefit to the specific participants taking the survey.

17.0 Data Management and Confidentiality

17.1 Describe the data analysis plan, including any statistical procedures or power analysis.

Our analysis plan includes three steps: 1) Evaluate reliability of translated scales; 2) Assess acceptability of the adapted intervention;

3) *Analyze stigma and related constructs pre- and post-intervention and between intervention sites. To ensure reliability of newly translated stigma scales, we will calculate Cronbach's alphas and compare the statistic for the Spanish version to the English version. To examine acceptability of the intervention, we will analyze post-FRESH questionnaire data on workshop satisfaction. We will use descriptive statistics for stigma outcomes and potential mediators and moderators of interest. We will compare changes from pre-FRESH to post-FRESH. Data from all time points will be used. Analyses will be performed for healthcare workers and people living with HIV separately and in aggregate. Analyses will include all participants who provide pre- and post-workshop data. Thus, final data will be presented as pre- and post-intervention changes in healthcare workers and people living with HIV. Estimates of correlations, intra-cluster correlation, within-period correlation, etc. will be calculated to inform future trial designs. Due to the small number of pilot participants, we will not conduct mediation analyses to examine pathways. We will conduct exploratory analyses of associations of potential mechanisms with outcome variables. HIV cascade outcomes will be compared pre- and post-intervention to provide guidance on the design of the future R01 trial. As a pilot study to develop preliminary estimates, this study is not powered to show efficacy. However, in preparation for the full-scale R01 trial, we conducted precision estimates for this study and a power analysis for the future R01.*

17.2 *Describe the steps that will be taken to secure the data (e.g., training, authorization of access, password protection, encryption, physical controls, certificates of confidentiality, and separation of identifiers and data) during storage, use, and transmission.*

17.3 *Describe any procedures that will be used for quality control of collected data.*

We are requesting IRB approval for data analysis and the final two steps of data collection including collecting anonymous, de-identified post-visit survey data from patients and providers and anonymous, de-identified medical records data. 1) Password-protected clinical records data will be delivered from the Dominican Republic to the United States via encrypted and secure box.net folder; once the data has been delivered to the folder, the FSU research team will verify the data and share with the biostatistician at the University of Alabama at Birmingham (UAB) for analyses. The UAB biostatistician is covered under the UAB IRB. There are no patient identifiers in the data. 2) Qualtrics data will be collected via the FSU approved Qualtrics system. Data will be downloaded intermittently during the two week data collection window into a secure box.net folder dedicated to these anonymous, identifier-less data. Once downloaded. The data will be password protected with a strong password and only shared for analysis purposes, as detailed

in the original proposal. No additional steps will be taken for quality control. These procedures led to successful outcomes for the prior three rounds of data collection without any breeches.

17.4 Describe how data or specimens will be handled study-wide:

- *What information will be included in that data or associated with the specimens?*
- *Where and how data or specimens will be stored?*
- *How long the data or specimens will be stored?*
- *Who will have access to the data or specimens?*
- *Who is responsible for receipt or transmission of the data or specimens?*
- *How data or specimens will be transported?*

N/A

18.0 Provisions to Monitor the Data to Ensure the Safety of Subjects

This section is required for any study that may involve any harm or discomfort for which the probability or magnitude is greater than those that may be ordinarily encountered by healthy persons in daily life or during the performance of routine physical or psychological examinations or test.

A DSMB was not required by the NIH. Because data collection is anonymous and de-identified, there is no way to map back to individuals. The medical records data contain limited information, none of which would indicate an AE or SAE, since the data is purely administrative. However, in-clinic data is being collected from patients and providers. These data are also anonymous and therefore unidentifiable; these data primarily focus on experiences of stigma and discrimination in the clinic setting. Upon the completion of the study, findings will be reported to the clinics.

19.0 Provisions to Protect the Privacy Interests of Subjects

19.1 Describe the steps that will be taken to protect subjects' privacy interests. "Privacy interest" refers to a person's desire to place limits on whom they interact or whom they provide personal information.

FSU study personnel will not have contact with participants.

19.2 Describe what steps you will take to make the subjects feel at ease with the research situation in terms of the questions being asked and the procedures being performed. "At ease" does not refer to physical discomfort, but the sense of intrusiveness a subject might experience in response to questions, examinations, and procedures.

FSU study personnel will not have contact with participants.

19.3 Indicate how the research team is permitted to access any sources of information about the subjects.

All remaining data is anonymous.

20.0 Compensation for Research-Related Injury

This section is required for any study that may involve any harm or discomfort for which the probability or magnitude is greater than those that may be ordinarily encountered by healthy persons in daily life or during the performance of routine physical or psychological examinations or test.

20.1 Describe the available compensation in the event of research related injury.

N/A

20.2 Provide a copy of contract language, if any, relevant to compensation for research-related injury.

N/A

21.0 Economic Burden to Subjects

21.1 Describe any costs that subjects may be responsible for because of participation in the research.

N/A

22.0 Consent Process

22.1 Indicate whether you will you be obtaining consent, and if so describe:

FSU study personnel will not be consenting participants. All consenting will be done by the Dominican Republic team, who have IRB approval at UNIBE.

23.0 Process to Document Consent in Writing

23.1 Describe whether you will be following “SOP: Written Documentation of Consent (HRP-091).” If not, describe whether and how consent of the subject will be documented in writing.

FSU study personnel will not be consenting participants. All consenting will be done by the Dominican Republic team, who have IRB approval at UNIBE.

24.0 Setting

24.1 Describe the sites or locations where your research team will conduct the research.

- Identify where your research team will identify and recruit potential subjects.*

Lotes y Servicios and Centro Sanitario in the Dominican Republic

- *Identify where research procedures will be performed.*

Lotes y Servicios and Centro Sanitario in the Dominican Republic

- *Describe the composition and involvement of any community advisory board.*

N/A at FSU.

- *For research conducted outside of the organization and its affiliates describe:*

- *Site-specific regulations or customs affecting the research for research outside the organization.*

None noted; any relevant considerations were addressed in the local IRB review by UNIBE.

- *Local scientific and ethical review structure outside the organization.*

IRB at UAB (Alabama) and UNIBE (Dominican Republic).

- *Describe non-FSU site approval to conduct research at any non-FSU site or location, and attach approval documentation. If no such approval was required, so state and be prepared to provide documentation. Studies involving non-FSU sites, institutions or agencies, such as TMH, CRMC, FAMU, state agencies and other organizations, may require those sites' IRB, research review or other approvals. Before submitting your studies for FSU IRB review, you must contact such sites to ascertain their review requirements and comply accordingly. The FSU IRB may require documentation of such site contact. Collaborations involving TMH are subject to specific requirements; click [here](#) for more information.*

We have received IRB approvals from UAB (Alabama) and UNIBE (Dominican Republic). See letters.

25.0 Resources Available

Adapting the Finding Respect and Ending Stigma around HIV (FRESH) Intervention for the Dominican Republic

25.1 Describe the resources available to conduct the research: For example, as appropriate:

- *Justify the feasibility of recruiting the required number of suitable subjects within the agreed recruitment period. For example, how many potential subjects do you have access to? What percentage of those potential subjects do you need to recruit?*
- *Describe the time that you will devote to conducting and completing the research.*
- *Describe your facilities.*
- *Describe the availability of medical or psychological resources that subjects might need as a result of an anticipated consequences of the human research.*
- *Describe your process to ensure that all persons assisting with the research are adequately informed about the protocol, the research procedures, and their duties and functions.*

N/A at FSU

Statistical Analysis Plan, Overall

Our analysis plan includes three steps: 1) Evaluate reliability of Spanish translated stigma scales; 2) Assess acceptability of the adapted intervention; 3) Analyze stigma and related constructs pre- and post-intervention and between intervention sites. To ensure reliability of newly translated stigma scales, we will calculate Cronbach's alphas and compare the statistic for the Spanish version to the English version. To examine acceptability of the intervention, we will analyze post-FRESH questionnaire data on workshop satisfaction. We will use descriptive statistics for stigma outcomes and potential mediators and moderators of interest. We will compare changes from pre-FRESH to post-FRESH. Data from all time points will be used. Analyses will be performed for healthcare workers and people living with HIV separately and in aggregate. Analyses will include all participants who provide pre- and post-workshop data. Thus, final data will be presented as pre- and post-intervention changes in healthcare workers and people living with HIV. Estimates of correlations, intra-cluster correlation, within-period correlation, etc. will be calculated to inform future trial designs. Due to the small number of pilot participants, we will not conduct mediation analyses to examine pathways. We will conduct exploratory analyses of associations of potential mechanisms with outcome variables. HIV cascade outcomes will be compared pre- and post-intervention to provide guidance on the design of the future R01 trial. As a pilot study to develop preliminary estimates, this study is not powered to show efficacy. However, in preparation for the full-scale R01 trial, we conducted precision estimates for this study and a power analysis for the future R01.

Statistical Analysis Plan, Primary Outcomes

While we will collect various forms of data, primary outcomes will be assessed from the pre-post workshop data. Cronbach's alphas will be calculated for each multi-item scale to examine for the internal consistency. Assumption of normality will be checked. Pre -and post- survey measures will then compare to assess the change after the workshop intervention using paired t-tests if the normality is confirmed, and Wilcoxon signed rank tests if the normality assumption was violated. The significance level will be $p<0.05$. All analyses will be performed with SAS (Version 9.4, Cray, North Carolina, USA), but SPSS can be used in its place if needed.

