The Finding Respect and Ending Stigma around HIV (FRESH) intervention is ideal to adapt and test. The FRESH intervention was originally developed in a study in five African nations,30 then was adapted for the United States. Since we have data showing that FRESH is adaptable, revising it for Latinx and Hispanic populations could yield scientific evidence leading FRESH to become a validated multi-region stigma-reduction intervention. The FRESH intervention brings together HWs of all types and PLWH to collaborate in a workshop to increase understanding of HIV-related and intersectional stigmas. FRESH facilitates conversations on effects of stigma on health and well-being and guides participants to better recognize and understand stigmas. FRESH includes didactic content and interactive activities. Each topic includes contact-theory informed activities designed to bring HWs and PLWH together to change perceptions of each other while enhancing empowerment and empathy. Facilitators use a standard manual for consistent content delivery. FRESH was efficacious in reducing stigmas in Africa, and the United States pilot had promising results (Preliminary Studies). We are confident that FRESH is an excellent intervention to adapt for the DR because, 1) FRESH is sustainable. Facilitators can train other trainers. 2) FRESH is low-cost. As a socio-structural intervention, there are no clinical costs. 3) FRESH is extensible. We have shown that FRESH was adapted from African contexts to the United States, and 4) FRESH is flexible. FRESH was adapted to address a spectrum of relevant intersectional stigmas in the US Deep South, among other modifications.

16. Participants (Screening and Selection)

a. How many participants are to be enrolled at UAB (if other sites relying on UAB IRB, list the number for each site)? **0**

If multi-site study, total number at all sites/institutions:

40 in intervention workshops; half providers and half PLWH clients.

b. Describe the characteristics of anticipated or planned participants (if multiple groups, repeat list for each group).

PLWH participants

Sex: **all**

Race/Ethnicity: **all**

Age: **16+**

Health status: **HIV positive**

healthcare workers

Sex: **all**

Race/Ethnicity: **all**

Age: **18+**

Health status: **not applicable**

c. From what population(s) will the participants be derived?

Healthcare workers and patients from the clinics in the DR

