The DR sites will be randomly assigned. Site 2 will be the site randomized to receive the adapted FRESH intervention first. Site 3 will receive the FRESH intervention at a later date. 10 sexual and gender minority PLWH and 10 HW will participate in the workshop at each site (total n from both sites=40). From workshop participants, we will collect pre- (N=40) and post- (N=40) surveys to assess satisfaction, feasibility, acceptability. We will collect outcome information on demographics, stigma-related measures, and HIV-related behavioral outcomes by asking all HWs and PLWH in Site 2 and 3 clinics.

UAB specific research activities include: traveling to DR sites to provide training on FRESH and the adapted FRESH, overseeing FRESH workshop implementation, possibly interacting with study participants participating in workshops and surveys, receiving all study data, data analysis, manuscript writing, presentations.

b. What is the probable length of time required for the entire protocol (i.e., recruitment through data analysis to study closure)? **4 years**

c. What is the total amount of time each participant will be involved? **12 months**

d. If different phases are involved, what is the duration of each phase in which the participants will be involved? If no phases are involved, enter "None." None

e. List the procedures, the length of time the procedure takes, the total # of times the procedure is performed, and indicate whether each is performed solely for research or would already be performed for treatment or diagnostic purposes (routine care) for the population.

-Insert additional table rows as needed.

-If procedure is sometimes research and sometimes routine care, include on separate lines with number of times as each.

Procedure	Length of Time Required of Participants	Total # of Times the Procedure is Performed	Research (Res) –OR- Routine Care
Site 1: focus group	1 hour	1	 Res  Routine
Site 1: in-depth interviews	1 hour	1	 Res  Routine
Site 1: feedback on adapted intervention	1 hour	2	 Res  Routine
Site 2: pre-workshop stigma surveys	30 minutes	2	 Res  Routine

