Site 2: workshop participation	16 hours	1	 Res  Routine
Site 2: post-workshop stigma-related surveys	30 minutes	2	 Res  Routine
Site 3: pre-workshop stigma surveys	30 minutes	2	 Res  Routine
Site 3: workshop participation	16 hours	1	 Res  Routine
Site 3: post-workshop stigma-related surveys	30 minutes	2	 Res  Routine

f. Will an interview script or questionnaire be used? Yes No

If Yes, attach a copy. All interviews/scripts will be submitted to UAB IRB via amendment once developed and approved by DR sites and IRB.

g. Will participants incur any costs as a result of their participation? Yes No

If Yes, describe the reason for and amount of each foreseeable cost. _____

h. Will participants be compensated? Yes No

If Yes, complete i-v.

i. Type: (e.g., cash, check, gift card, merchandise): cash

ii. Amount or Value: \$50 USD (distributed as DR currency)

iii. Method (e.g., mail, at visit): at visit

iv. Timing of Payments: (e.g., every visit, each month): each workshop day

v. Maximum Amount of Compensation per Participant: \$100 USD

18. Benefits

Describe the potential benefits of the research. Participants in this study are HWs and PLWH. If successful, this project will yield a model for sustainable implementation of an intervention to reduce stigma and improve outcomes across the HIV cascade in resource-poor settings. Given the limited risks associated with this intervention study, the benefits outweigh the risks. PLWH are at particular risk of being stigmatized, yet few interventions exist that specifically reduce stigma in healthcare settings for the Caribbean. This study will ultimately benefit both PLWH and their healthcare providers by creating stigma-free healthcare environments and improving outcomes along the HIV continuum of care.

19. Risks - in nontechnical, lay language

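### Do the paired-survey rule and the reliance on post-workshop satisfaction forms need added attendance counts and a missing-data check?

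*Combined protocol and SAP*

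**What the plan says.** The Statistical Analysis Plan, Overall, has three steps: reliability of the translated scales, acceptability of the adapted intervention, and change in stigma. Section 17.1 of the FSU protocol carries the same text.

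- On acceptability: "To examine acceptability of the intervention, we will analyze post-FRESH questionnaire data on workshop satisfaction".
- On the analysis set: "Analyses will include all participants who provide pre- and post-workshop data". The next sentence says that results will therefore be shown as pre-to-post changes in the two groups.
- On grouping: "Analyses will be performed for healthcare workers and people living with HIV separately and in aggregate".
- On purpose: "As a pilot study to develop preliminary estimates, this study is not powered to show efficacy".

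The Statistical Analysis Plan, Primary Outcomes, adds that "primary outcomes will be assessed from the pre-post workshop data", using a paired t-test or a Wilcoxon signed rank test.

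The planned numbers are in the UAB protocol. Item 16.a gives "40 in intervention workshops; half providers and half PLWH clients". Item 17.a says: "From workshop participants, we will collect pre- (N=40) and post- (N=40) surveys to assess satisfaction, feasibility, acceptability".

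Neither protocol nor the SAP asks for counts of starters, completers or returned forms, and none sets out a missing-data method.

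**The concern.** A satisfaction figure taken only from people who filled in the post form leaves out anyone who walked away. If those people were less satisfied, the figure is too high. A paired test likewise drops anyone without a second survey, so the mean change in stigma could be biased, in a direction that nobody can state beforehand.

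Partial attendance is possible. Item 17.e of the UAB protocol gives the workshop 16 hours, and item 17.h pays $50 for each workshop day up to $100, which implies $100/$50 = 2 paid days. Item 20.a lets participants stop at any time. The groups are small, so each missing person matters: 1/20 = 5 percentage points within a group and 1/40 = 2.5 points overall.

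The pilot is meant to inform a larger trial, which would need attendance and return rates. If the loss were real and unreported, acceptability could look better than it was.

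**Working it through.** **Planned number.** UAB protocol items 16.e and 17.a: 2 sites × (10 people living with HIV + 10 health workers) = 40. This reproduces the stated 40, with 20 in each group. The plan expects 40 pre and 40 post surveys, so it allows for no loss.

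**Which rule does what.** The both-surveys sentence sits with the change analysis and leads directly into how changes will be presented. The acceptability sentence does not require a pre survey. Someone who returns no post form is absent from the satisfaction result because no rating exists, not because a rule excludes it. Paired tests need complete pairs in any case.

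**Satisfaction, if forms were missing.** Assumptions: satisfaction is yes/no, and about 90% of respondents are satisfied. The documents give neither. With N starters, m missing and x satisfied among n = N − m, the all-starters bounds are x/N and (x + m)/N. The interval is the exact (Clopper-Pearson) 95% interval for x/n.

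| N | m | x/n | All-starters bounds | Exact 95% interval |
|---|---|---|---|---|
| 40 | 0 | 36/40 = 90.0% | 90.0% to 90.0% | 76.3% to 97.2% |
| 40 | 4 | 32/36 = 88.9% | 80.0% to 90.0% | 73.9% to 96.9% |
| 40 | 8 | 29/32 = 90.6% | 72.5% to 92.5% | 75.0% to 98.0% |
| 40 | 12 | 25/28 = 89.3% | 62.5% to 92.5% | 71.8% to 97.7% |
| 20 | 1 | 17/19 = 89.5% | 85.0% to 90.0% | 66.9% to 98.7% |
| 20 | 2 | 16/18 = 88.9% | 80.0% to 90.0% | 65.3% to 98.6% |
| 20 | 4 | 14/16 = 87.5% | 70.0% to 90.0% | 61.7% to 98.4% |
| 20 | 6 | 13/14 = 92.9% | 65.0% to 95.0% | 66.1% to 99.8% |

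Up to 10% loss overall and 20% within a group, the bounds lie inside the interval. With 8 of 40 missing, the lower bound is 75.0 − 72.5 = 2.5 points outside. With 6 of 20 missing it is 66.1 − 65.0 = 1.1 points outside. It is clearly outside only with 12 of 40 missing (71.8 − 62.5 = 9.3 points), and a loss of that size would be plain from an n of 28.

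**Stigma change, if pairs were missing.** Assume that completers change by 0.50 SD (SD of change).

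- Non-returners unchanged: 0.50 × 36/40 = 0.45 with 4 missing, and 0.50 × 32/40 = 0.40 with 8 missing. The shifts are 0.05 and 0.10 SD. The standard errors are 1/√36 = 0.167 and 1/√32 = 0.177 SD, so both shifts are below one standard error.
- Non-returners worsen by 0.50 SD, a harsher case: 0.45 − 0.05 = 0.40 with 4 missing, and 0.40 − 0.10 = 0.30 with 8 missing. The shifts are 0.10 and 0.20 SD. The second exceeds one standard error but is inside the 95% half-width of 0.361 SD at n = 32.
- Precision: going from 40 to 32 pairs widens the 95% half-width from 0.320 to 0.361 SD.

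**The case for a change.** The strongest reply is that a confidence interval covers random error only. Selective non-return is a separate uncertainty, and lying inside sampling error does not remove it. Feasibility and acceptability are central products of a pilot, so the lack of power for efficacy does not settle the matter. Item 17.a names feasibility, yet the SAP has no feasibility analysis. A reported n also does not separate people who left early from people who stayed but handed in no form. If everyone returned the form, the counts would show 40 of 40 and cost nothing.

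Much of this is fair as reporting advice. A table with the n of paired surveys and of satisfaction forms by group, plus attendance where it was recorded, would help a reader. It does not show that a stated rule gives a wrong result. Loss of forms can be read from n against 20, 20 and 40. Only attendance by day stays out of sight, and neither document describes an attendance log. The workshops are already over (FSU protocol, section 5.0), so wording in the SAP could not recover attendance that was never recorded.

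The possible extra analyses are matters of choice. Scoring non-returners at the extremes of the scale adds little at this sample size. Setting their stigma change to zero always pulls the mean towards zero, which does not fit a bias of unknown direction.

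**Conclusion.** The observation is accurate: the SAP does not ask for starters, completers or returns, and it has no missing-data check for the workshop surveys. It is a gap in detail that analysts fill by ordinary practice, reporting n with each descriptive summary and paired test against denominators that the UAB protocol already fixes. The both-surveys rule is what a paired analysis needs, and it does not cause the limits of the satisfaction data.

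The size is small under plausible loss. Under the stated assumptions, the all-starters bounds stay within sampling error with up to 4 missing overall or 4 within a group. They pass it by 2.5 points with 8 of 40 missing. With no loss, which is all that the documents imply, nothing changes.

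This rests on assumed loss rates, an assumed satisfaction rate near 90%, an assumed 0.50 SD change, and n being reported by group. It concerns only the workshop surveys. The anonymous in-clinic surveys and the clinic-level HIV care data are not affected. No stated threshold, power or error rate turns on the point, and no change to the plan is needed.

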1.0 Study Summary

Note: We are only applying for IRB approval for the remainder of the project. Most of the study has already been completed. (See UAB IRB protocol document for orientation.) We are only applying for the remainder of what was previously approved at UAB. We are not proposing any changes to the approval we had at UAB. All local personnel in the Dominican Republic are covered under the local reviewing IRB at UNIBE.

Study Title	Adapting the Finding Respect and Ending Stigma around HIV (FRESH) Intervention for the Dominican Republic
Study Design	Survey
Primary Objective	Analyze perceptions/attitudes/beliefs around HIV
Secondary Objective(s)	Health outcomes (per de-identified, anonymous clinical data)
Research Intervention(s)	N/A
Study Population	Clients and health workers
Sample Size	N=100 clients and N=20 health workers
Study Duration for individual participants	One time survey
Study Specific Abbreviations/ Definitions	PLWH: people living with HIV SGM: sexual and gender minorities MSM: men who have sex with men

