6.0 Procedures Involved

6.1 Describe and explain the study design.

The remainder of the study is a one-time survey for participants.

6.2 Provide a description of all research procedures being performed and when they are performed, including procedures being performed to monitor subjects for safety or minimize risks.

We will collect outcome information on demographics, stigma-related measures, and HIV-related behavioral outcomes by asking all HWs and PLWH in Site 2 and 3 clinics to complete in-clinic anonymous surveys (we expect the effects of the workshop to impact stigma throughout the whole clinic, not just the workshop participants). In-clinic stigma surveys will be completed at 4 time points pre- and post- workshop (intervention). Time points 1-3 have already been completed.

Research personnel at FSU will not be collecting data. However, the surveys, attached to this submission, will be held through FSU's Qualtrics forum. Research personnel at FSU will not have any way to identify the individual participants (i.e. no names or identifiers are being collected). All data collection methods will be done by the local team in the Dominican Republic, who have separate IRB approval at UNIBE.

In addition, outcomes related to HIV care will be collected from the national HIV medical records system monthly. Data will include 1) Number of new-to-care PLWH, 2) ART initiation, and 3) Viral load

Adapting the Finding Respect and Ending Stigma around HIV (FRESH) Intervention for the Dominican Republic

suppression rates. These data will be used to compare site-level HIV cascade outcomes pre- and post- FRESH. This data is de-identified and will be collected by the local team in the Dominican Republic. There is no way to trace data to individuals, as the data will be collected through the Ministry of Health. FSU personnel, if approved, will receive the anonymous data from the local Dominican Republic team.

6.3 Describe:

- *Procedures performed to lessen the probability or magnitude of risks.*
- *The source records that will be used to collect data about subjects. (Attach all surveys, scripts, and data collection forms.)*

All data collection is anonymous. There is no way to trace data to back individuals. Contact with human subjects will not be done through FSU.

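### Monthly HIV-cascade outcomes are compared only before v after FRESH, leaving calendar trend uncontrolled, although a randomised later-start clinic supplies concurrent months (minor)

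*Combined protocol and SAP*

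**What the plan says.** The UAB protocol (items 16.e and 17.a) randomises the order of start: Site 2 receives the workshop first and Site 3 is a delayed-start site. The FSU protocol (section 6.2) has new-to-care numbers, ART initiation and viral suppression drawn monthly from the national records system. Section 12.1 adds that these are clinic-level figures covering 24 months.

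The analysis of these data is stated three times, each time as before against after. Section 6.2: "These data will be used to compare site-level HIV cascade outcomes pre- and post- FRESH". Section 17.1 and the Statistical Analysis Plan, Overall: "HIV cascade outcomes will be compared pre- and post-intervention to provide guidance on the design of the future R01 trial". None of the three gives an estimator, a rule assigning months to the before or after period, a calendar term, or a comparison with the clinic not yet exposed.

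Two nearby sentences might seem to fill the gap. Step 3 of the SAP reads "Analyze stigma and related constructs pre- and post-intervention and between intervention sites", but it covers stigma and related constructs, not the cascade outcomes. The SAP also says "Estimates of correlations, intra-cluster correlation, within-period correlation, etc. will be calculated to inform future trial designs". Those are planning parameters, not an adjustment for calendar time.

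**The concern.** A before/after comparison at a clinic attributes to the intervention whatever else changed over the same months: treatment supply, national policy, testing campaigns, record completeness. A staggered start offers a partial remedy. While Site 2 is exposed and Site 3 is not, Site 3 shows what happened over the same months without FRESH. The plan collects that series but does not say it will be used.

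The cascade comparison has one declared purpose, which is to guide the R01. A change that mixes trend with intervention could lead the R01 team to plan around an effect that is too large or, if care was deteriorating, too small.

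**Working it through.** The plan states no effect, precision or variance for the cascade outcomes, so there is no figure to reproduce. Taken from the documents: 24 monthly points per clinic, two clinics, Site 2 before Site 3. Not in the documents, and assumed below: the trend b, the workshop months, the monthly residual SD σ, and any autocorrelation.

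**1. Trend carried into a pre/post difference.** Suppose months 1 to m are before the workshop and m+1 to 24 are after. The mean calendar month is (m+1)/2 before and (m+25)/2 after. The difference is 24/2 = 12 months whatever m is. With no FRESH effect, post minus pre is therefore 12b at each clinic:

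- b = 0.1 point/month: 1.2 points
- b = 0.25: 3 points
- b = 0.5: 6 points

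With windows of k months either side of the workshop, the two means are k months apart and the difference is k × b. For example, k = 3 and b = 0.25 give 0.75 points.

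**2. What the staggered contrast removes.** Take Site 2's change minus Site 3's change, using only months before Site 3's workshop. Let p be the months before Site 2's workshop and g the months between the two workshops. A trend common to both clinics cancels. If the clinics' trends differ by d per month, a bias of d(p+g)/2 remains.

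**3. Its precision.** With independent monthly errors, SE = σ√[2(1/p + 1/g)] on p+g−2 residual degrees of freedom. Half-widths are for 95% t intervals.

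| Assumed workshop months (Site 2/Site 3) | p, g | SE (σ) | df | Half-width (σ) | Half-width, AR(1) 0.5 (σ) | Bias from d |
|---|---|---|---|---|---|---|
| 7/13 | 6, 6 | 0.82 | 10 | 1.82 | 2.59 | 6d |
| 9/15 | 8, 6 | 0.76 | 12 | 1.66 | 2.43 | 7d |
| 10/13 | 9, 3 | 0.94 | 10 | 2.10 | 2.76 | 6d |
| 12/18 | 11, 6 | 0.72 | 15 | 1.53 | 2.28 | 8.5d |
| 13/16 | 12, 3 | 0.91 | 13 | 1.97 | 2.62 | 7.5d |

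With Site 2 starting in month 7, 10 or 13 and independent errors, a gap of one month gives half-widths of 3.2 to 3.9σ, and a gap of two months gives 2.4 to 2.8σ.

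Setting d(p+g)/2 equal to 12b shows that the contrast is less biased than the full-period difference only while d is below about 1.4b (12/8.5) to 2.0b (12/6).

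**4. Total error.** Assume σ = 5 points, independent errors and d = 0. For 7/13, the SE of the pre/post difference averaged over the two clinics is 5 × ½√(1/6 + 1/18 + 1/12 + 1/12) = 1.56. Its root mean squared error is √(1.56² + (12b)²):

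- b = 0.1: 2.0 points
- b = 0.25: 3.4 points
- b = 0.5: 6.2 points

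The staggered contrast has 0.816 × 5 = 4.1 points at every b. Across the five pairs it runs from 3.6 to 4.7 points. On these inputs pre/post has the smaller total error at b = 0.25 or less, and the staggered contrast has the smaller at b = 0.5.

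**The case against.** The strongest reply is that the plan is brief rather than wrong. No estimator is named, and the wording would also fit a plotted or segmented monthly series, or short windows around each workshop. That stands against treating 12b as the plan's bias: it is the result under one reading. It does not meet the point that none of the three statements provides for calendar time or for the unexposed clinic.

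Second, the alternative is weak. With one clinic per sequence, randomising the order cannot balance clinic-specific trends or shocks. There are only two possible orders, so the smallest one-sided randomisation p-value is 0.5. Total error can also be larger than for pre/post. All of this stands, and it is why the contrast can only be an addition.

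Third, the stated purpose is modest: a pilot not powered for efficacy, with primary outcomes taken from the workshop surveys. This also stands, and it sets the severity. The SAP mentions precision estimates and an R01 power analysis, and section 17.3 refers to an original proposal. None of these is among the documents, and they may say more.

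A reader might go further and infer that the in-clinic surveys cannot support any between-site comparison, because the procedure table lists two rounds before and two after at each site. That needs the table to describe the in-clinic rounds and both clinics to share one calendar. The documents state neither, and the between-site step may mean no more than description by site.

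**Conclusion.** The point holds as a minor one. As written, the cascade comparison leaves calendar trend uncontrolled and does not use concurrent unexposed months that the design provides. The size is unknown because b is not given. It is 12b under full-period means and k × b under k-month windows, assuming a linear trend common to both clinics.

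Two stronger readings are not supported. One is that the trial's main result is compromised: the primary analysis is a paired comparison of workshop surveys, a different data source to which the 24-month arithmetic does not apply. The other is that the plan will produce false-positive cascade findings: no hypothesis test is stated for those outcomes, and the 0.05 level appears only under the primary outcomes. What is at risk is the interpretation of a secondary figure used to plan the R01.

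**What to change.** 1. Plot each monthly cascade outcome by clinic over the 24 months, with each clinic's workshop date marked.
2. Wherever pre/post cascade changes are used to guide the R01, label them as uncontrolled for calendar time.
3. Alongside pre/post, report one descriptive contrast with an interval: Site 2's change minus Site 3's change, using only months before Site 3's workshop. State that it was specified late, since by the FSU protocol's own account "Most of the study has already been completed". State also that it assumes parallel trends, rests on one clinic per sequence, and is not a test of efficacy.

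The cost is a few sentences in the SAP, the two workshop dates, one plot per outcome and one simple calculation, with no new data. The drawback is imprecision: about ±1.5 to 2.1 monthly residual SDs on the assumed start months with independent errors, and wider with autocorrelation or a short gap between starts. If the trend is small, the contrast may be further from the truth than pre/post, so both should be shown and read against the plot.
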